### 6.6.1.2.2. ITT for Primary Efficacy Endpoint

#### 6.6.1.2.2.1. Estimand Strategy

Same as [Section 6.6.1.1.1](#).

#### 6.6.1.2.2.2. Population of Interest

ITT population will be used as defined in [Section 5.2.1](#).

#### 6.6.1.2.2.3. Intercurrent Event Handling Strategy

Same as [Section 6.6.1.1.3](#).

**6.6.1.2.2.4. Analysis Variable**

Same as [Section 6.6.1.1.4](#).

**6.6.1.2.2.5. Population Summary for Treatment Comparison**

Same as [Section 6.6.1.1.5](#).

**6.6.1.2.3. MI ANCOVA**

Multiple Imputation Analysis of Covariance model (MI ANCOVA) will be performed to evaluate the robustness of the primary analysis as a sensitivity analysis.

**6.6.1.2.3.1. Estimand Strategy**

Same as [Section 6.6.1.1.1](#)

**6.6.1.2.3.2. Population of Interest**

Same as [Section 6.6.1.1.2](#)

**6.6.1.2.3.3. Intercurrent Event Handling**

Under the MAR assumption, subjects who discontinued from the treatment early alive are assumed to have the same data pattern as subjects who remain in the study for the same treatment arm. Multiple imputation will be carried out to impute missing data for visits up to Week 52.

Death: Same as [Section 6.6.1.1.3](#).

**6.6.1.2.3.4. Analysis Variable**

Same as Section 6.6.1.1.4 (Missing value imputation rules are defined below).

**6.6.1.2.3.5. Population Summary for Treatment Comparison**

The combined treatment difference of LSMean (and SE) and the corresponding 95% CI for the estimated change from baseline in PUL total score at Week 52 will be presented.

Analysis will be performed in 3 steps.

Step 1a - First, the intermittent missing PUL data will be imputed for each treatment relying on non-missing data from all subjects within each treatment group using the Markov Chain Monte Carlo (MCMC) imputation model with baseline PUL and other baseline factors, and the available non-missing PUL to generate a monotone missing data pattern that only has missing data at end for planned visits through Week 52. The reported (observed) value will be used for multiple imputation. Change from baseline values will be derived using the difference between the imputed or observed post-baseline values and baseline values.

Step 1b - Then, for each of the 200 datasets with monotone missing data generated above, missing data at end through Week 52 will be imputed to derive 200 imputed datasets with non-missing data.

Sample SAS code:

```
/*examine missing patterns*/
```

```

PROC MI DATA = INDAT NIMPUTE = 0;
  BY TRTPN;
  VAR BASE WEEK16 WEEK28 WEEK40 WEEK52;
RUN;

```

Suppose the output from PROC MI above indicates that the missing pattern is non-monotone, it is necessary to perform Step 1a, which is Partial imputation (just enough to get the monotone missing pattern).

```

/*partial imputation to get monotone missing pattern*/
PROC MI DATA= INDAT OUT=xx1 SEED=9978991 NIMPUTE=200 OUT = MONO;
  BY TRTPN;
  VAR BASE WEEK16 WEEK28 WEEK40 WEEK52;
  MCMC CHAIN=multiple IMPUTE=monotone;
RUN;

/*The above procedure will output MONO dataset with a monotone missing data pattern. */
PROC SORT DATA= MONO OUT =XX1;
  BY _IMPUTATION_;
RUN;

```

```

PROC MI DATA=XX1 OUT=XX SEED=9978 NIMPUTE=1;
  BY _IMPUTATION_;
  VAR TRTPN BASE WEEK16 WEEK28 WEEK40 WEEK52;
  CLASS TRTPN;
  MONOTONE REGRESSION (/details);
RUN;

```

```

DATA MIANCOVA;
  SET XX;
  CHG_WK52= WEEK52 - BASE;
RUN;

```

Step 2 - The 200 multiple-imputation datasets with imputed and observed PUL data at Week 52 will be analyzed separately for each imputation using the ANCOVA method. The ANCOVA model will contain terms for treatment, baseline PUL measurements. The LSMean and corresponding SE for the change from baseline in PUL total score at Week 52 will be estimated.

Sample SAS code:

```

PROC MIXED data= MIANCOVA;
  BY _IMPUTATION_;
  CLASS TRTPN ItemAgrp;
  MODEL CHG_WK52 = TRTPN ItemAgrp COVARIATES/SOLUTION DDFM=KR;
  LSMEANS TRTPN / PDIFF CL;
  ODS OUTPUT DIFFS=LSDIFS LSMEANS=LSM SOLUTIONF=PARMS;
RUN;

```

Step 3 - The SAS PROC MIANALYZE will be used to derive the final estimates and test statistics summarizing the 200 analysis results.

Sample SAS code:

```
PROC SORT DATA=LSM;  
  BY TRTPN;  
RUN;
```

```
PROC MIANALYZE DATA=LSM;  
  BY TRTPN;  
  MODELEFFECTS ESTIMATE;  
  STDERR;  
  ODS OUTPUT ParameterEstimates=LSM2;  
RUN;
```

```
PROC MIANALYZE DATA= LSDIFS;  
  MODELEFFECTS ESTIMATE;  
  STDERR;  
  ODS OUTPUT ParameterEstimates=lsdiffs2;  
RUN;
```

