### 3.3. Sample Size Determination

This section is updated based on latest publications and the study enrollment.

This study is planned to enroll a total of approximately 92 subjects with a 1:1 randomization ratio of assigning to pamrevlumab or placebo, respectively. With Performance of Upper Limb (PUL) version 2.0, the sample size of 92 subjects is needed to detect a treatment difference of 2.0 between treatment arms in change from baseline in the total score of PUL at Week 52, assuming a standard deviation of 2.9 with a 90% power, based on a two-sided two-sample t-test at the alpha level of 0.05. A sample size of 82 subjects will provide the study with at least 85% power to detect the same assumed treatment difference.

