#### 6.6.1.2.4.5. Population summary for treatment comparison

Under the jump-to-control assumption, the analysis will be carried out in 3 steps.

Step 1 - the missing PUL data will be imputed to derive 200 imputed datasets with non-missing data according to the jump-to-control data pattern.

Sample SAS code:

```
PROC MI DATA=aval OUT=xx SEED=8767892 NIMPUTE=200;
  CLASS TRTP;
  VAR BASE WEEK16 WEEK28 WEEK40 WEEK52;
  MONOTONE REG(/details);
  MNAR MODEL (WEEK52/MODELOBS=(TRTP='Placebo'));
RUN;
```

Step 2 - The 200 multiple imputation datasets with imputed and observed data will be analyzed separately using the ANCOVA method separately as described in [Section 6.6.1.2.3.5](#). The LSMean and corresponding SE for the change from baseline in PUL total score at Week 52 will be estimated.

Step 3 - The SAS PROC MIANALYZE will be used to derive the final estimates and test statistics summarizing the 200 dataset results.

The combined treatment difference of LSMean, corresponding SE and 95% CI for the estimated change from baseline in PUL total score at week 52 will be presented.

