#### 6.6.1.2.5.5. Population summary for treatment comparison

The integrated treatment difference of LSMean, corresponding SE and 95% CI for the change from baseline in PUL total score at week 52 will be presented.

The multiple imputation analysis will be performed as follows.

Step 1 - the missing PUL data will be imputed to derive 200 imputed datasets with non-missing data according to the delta-adjusting data approach.

Sample SAS code:

```
PROC MI DATA=aval OUT=zz SEED=9876783 NIMPUTE=200;
  CLASS TRTP;
  VAR TRTP BASE WEEK16 WEEK28 WEEK40 WEEK52;
  MONOTONE REG;
  MNAR ADJUST (WEEK16 /SHIFT=-## ADJUSTOBS =(TRTP='pamrevlumab'));
  MNAR ADJUST (WEEK28 /SHIFT=-## ADJUSTOBS =(TRTP='pamrevlumab'));
  MNAR ADJUST (WEEK40 /SHIFT=-## ADJUSTOBS =(TRTP='pamrevlumab'));
  MNAR ADJUST (WEEK52 /SHIFT=-## ADJUSTOBS =(TRTP='pamrevlumab'));
RUN;
```

Step 2- The observed and imputed PUL data will be analyzed using the ANCOVA method separately as described in [Section 6.6.1.2.3.5](#) for each of the 200 imputed datasets. The LSMean and corresponding SE for the change from baseline in PUL at week 52 will be estimated.

Step 3- The SAS PROC MIANALYZE will be used to summarize the final estimates and test statistics from the 200 dataset results.

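### The MI ANCOVA pooling code drops the small-sample degrees of freedom, so its interval is about 2% narrower than the SAP's own Kenward-Roger choice implies

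*SAP*

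**What the plan says.** SAP 6.6.1.2.3.5 describes the MI ANCOVA sensitivity analysis in three steps: impute 200 datasets, fit an ANCOVA to each, and pool.

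- **Step 2 (sample code):** "MODEL CHG_WK52 = TRTPN ItemAgrp COVARIATES/SOLUTION DDFM=KR". The df method is Kenward-Roger.
- **Step 3 (sample code):** two pooling calls, one for the arm means and one for the difference. The latter is "PROC MIANALYZE DATA= LSDIFS". Both pass only the estimate and its standard error. Neither has an EDF= option, and no text in the SAP sets a df for pooling.
- **Jump-to-control, 6.6.1.2.4.5:** "The SAS PROC MIANALYZE will be used to derive the final estimates and test statistics summarizing the 200 dataset results". No pooling code is shown.
- **Delta-adjusting (tipping point), 6.6.1.2.5.5:** "The SAS PROC MIANALYZE will be used to summarize the final estimates and test statistics from the 200 dataset results". Again no pooling code.

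The last two sections refer back to 6.6.1.2.3.5 for the ANCOVA step only. Kenward-Roger df are also requested for the primary random coefficient model (6.6.1.1.5), the MMRM (6.6.1.2.1.5), grip strength (6.6.2.2.3) and LVEF (6.6.2.3.3).

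**The concern.** The Step 2 model has no RANDOM or REPEATED statement. Kenward-Roger therefore leaves the standard error unchanged and serves only to set the reference df. Step 3 discards those df, so the request has no effect on the pooled result. The pooled interval uses an almost normal quantile although the analysis set has only 82 subjects.

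These analyses are meant to show whether the primary result survives different assumptions about missing data. The df matter most for the delta-adjusting analysis: its result is the shift at which significance is lost, so it depends directly on the critical value.

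**Working it through.** **Inputs from the documents.** SAP 3.3 gives "1:1 randomization ratio", "detect a treatment difference of 2.0 between treatment arms", "assuming a standard deviation of 2.9 with a 90% power" and "based on a two-sided two-sample t-test at the alpha level of 0.05". SAP 7 gives an mITT set of 82 with 87% power. SAP 6.6.1.2.3.5 gives m = 200. SAP 5.2.2 and Appendix 3 leave five entry-score levels, 2 to 6.

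**Assumed.** The documents give no dropout rate or fraction of missing information λ, so λ was varied from 5% to 30%. That the procedure treats complete-data df as infinite when EDF= is absent is standard software behaviour; the SAP does not state it.

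**The plan's own figures first.** Noncentral t, 46 per arm: power 90.5%. With 41 per arm: SE = 2.9 × √(2/41) = 0.64 and power 87.0%. Both stated figures reproduce.

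**Complete-data df, v₀, at N = 82.** The prose and the code name different terms, so three cases are needed:
- treatment and baseline PUL: 82 − 3 = 79
- treatment and five entry levels: 82 − 6 = 76
- treatment, five entry levels and baseline PUL: 82 − 7 = 75

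**Pooled df without EDF= (Rubin):** (m − 1)/λ². At λ = 10%: 199/0.01 = 19,900.

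**Pooled df with EDF= (Barnard-Rubin):** df_obs = [(v₀ + 1)/(v₀ + 3)] × v₀ × (1 − λ), then 1/(1/df_Rubin + 1/df_obs). At v₀ = 76 and λ = 10%: df_obs = (77/79) × 76 × 0.9 = 66.7, giving 66.4.

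Cells with three entries are for v₀ = 79 / 76 / 75. The last column is the p-value reported without EDF= when the p-value with EDF= is 0.050.

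| λ | df without EDF= | 97.5% quantile | df with EDF= | 97.5% quantile | Narrower by (%) | Reported p |
|---|---|---|---|---|---|---|
| 5% | 79,600 | 1.9600 | 73.2 / 70.3 / 69.4 | 1.9929 / 1.9943 / 1.9948 | 1.65 / 1.72 / 1.74 | 0.0463 / 0.0461 / 0.0461 |
| 10% | 19,900 | 1.9601 | 69.1 / 66.4 / 65.6 | 1.9949 / 1.9963 / 1.9968 | 1.74 / 1.81 / 1.84 | 0.0461 / 0.0459 / 0.0459 |
| 20% | 4,975 | 1.9604 | 60.9 / 58.6 / 57.8 | 1.9997 / 2.0013 / 2.0019 | 1.96 / 2.04 / 2.07 | 0.0456 / 0.0454 / 0.0454 |
| 30% | 2,211 | 1.9610 | 52.7 / 50.7 / 50.0 | 2.0060 / 2.0079 / 2.0086 | 2.24 / 2.33 / 2.37 | 0.0450 / 0.0448 / 0.0447 |

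With SE 0.64, the interval half-width moves from about 1.255 to 1.276–1.286 PUL points.

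**Rough size at the tipping point (v₀ = 76).** For λ of 5% to 20% the quantile gap is 0.034 to 0.041. Times 0.64, that is 0.022 to 0.026 PUL points in the treatment difference. If the same 5% to 20% of pamrevlumab Week 52 values are imputed, the net shift in those values changes by 0.022/0.05 = 0.44 down to 0.026/0.20 = 0.13 points. This ignores the rise in SE with missing data and the shifts applied at earlier visits.

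**Simulated type I error (null, N = 82, m = 200, 10,000 trials per setting, Monte Carlo SE about 0.002).** The model was simplified: normal outcomes, one early visit as auxiliary, and treatment and baseline in the ANCOVA.

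| Week 52 missing | MAR, without / with EDF= | Jump-to-control, without / with EDF= |
|---|---|---|
| 5% | 0.051 / 0.048 | 0.040 / 0.037 |
| 10% | 0.053 / 0.048 | 0.035 / 0.031 |
| 20% | 0.050 / 0.046 | 0.018 / 0.015 |
| 30% | 0.046 / 0.041 | 0.012 / 0.011 |

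A larger MAR simulation (60,000 trials per setting, 2% to 20% missing) gave 5.2% to 5.5% without EDF= and 4.8% to 5.1% with it. Delta-adjusting was not simulated.

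**The case against.** A reader might infer that all three multiple-imputation analyses are anti-conservative, or that they are held to a looser standard than the primary. The evidence does not support that.

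- **Error rates.** Taking the pooled statistic to follow the small-sample t exactly gives a type I error of about 5.4% to 5.6%, but that is a tail calculation. Simulated MAR error stays close to 5% with or without the option. Jump-to-control is conservative even without it, because Rubin's variance overstates the true variance: at 10% missing, the mean SE was 0.681 against an empirical SD of 0.615. This stands.
- **Scope.** The omission is visible in code for MI ANCOVA only. For the other two analyses it is an inference. This stands.
- **Sample code.** The code is labelled as such and is plainly illustrative: it has placeholders for the covariates and the shift values. The Step 3 prose does not commit to large-sample df. This stands in part, but the code is the only place where the SAP specifies pooling, and a programmer who follows it gets the default.
- **Materiality.** These are sensitivity analyses outside the Table 1 testing sequence, with no decision rule attached. This stands and limits the point to a minor one.

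**Conclusion.** The point holds as a small inconsistency in specification. As coded, MI ANCOVA pools with df in the thousands instead of roughly 50 to 73. The consequence is an interval about 1.6% to 2.4% narrower than the SAP's chosen df method implies, which could matter only for a borderline sensitivity result or for the exact location of a tipping point. It is not evidence of general anti-conservatism, and it does not touch the primary analysis, whose model keeps its Kenward-Roger df.

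The size rests on N = 82, on complete-data df of 75 to 79 with all five entry levels populated, on an assumed 5% to 30% missing information, and on the software default.

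**What to change.** 1. Settle the ANCOVA terms in 6.6.1.2.3.5, where prose and code differ, so that the residual df is defined.
2. Add EDF= equal to that residual df to both pooling calls in Step 3, for the arm means and for the difference.
3. State that the same pooling call is used in 6.6.1.2.5.5, where the critical value determines the tipping point, and in 6.6.1.2.4.5 for consistency.

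The cost is one option per call and a sentence in each of two sections, made before unblinding. Intervals become about 2% wider. Jump-to-control becomes slightly more conservative, for example 3.1% instead of 3.5% in the simulation at 10% missing.

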#### **6.6.1.2.4. Pattern Mixture Models under MNAR for Missing Data: Jump-to-Control Analysis**

The goal of the following analyses is to address the possibility of data being missing not at random (MNAR).

##### **6.6.1.2.4.1. Estimand Strategy**

Same as [Section 6.6.1.1.1](#)

##### **6.6.1.2.4.2. Population of Interest**

Same as [Section 6.6.1.1.2](#)

##### **6.6.1.2.4.3. Intercurrent Event Handling**

Treatment discontinuation (such as due to AEs, lost to follow-up, withdrawal by subject, physician decision, protocol deviations, etc.): The missing data pattern for the pamrevlumab subjects after withdrawal from the study can be assumed to switch to the same data pattern as subjects on the placebo treatment. Subjects that discontinued from the placebo arm are assumed to have the same data pattern as placebo subjects that remain in the study. This is often called the jump-to-control approach.

Death: same as [Section 6.6.1.1.3](#).

##### **6.6.1.2.4.4. Analysis Variable**

Change from baseline in the total score of all PUL assessments at Week 52 (Missing value imputation rules are defined below).

#### 6.6.1.2.4.5. Population summary for treatment comparison

Under the jump-to-control assumption, the analysis will be carried out in 3 steps.

Step 1 - the missing PUL data will be imputed to derive 200 imputed datasets with non-missing data according to the jump-to-control data pattern.

Sample SAS code:

```
PROC MI DATA=aval OUT=xx SEED=8767892 NIMPUTE=200;
  CLASS TRTP;
  VAR BASE WEEK16 WEEK28 WEEK40 WEEK52;
  MONOTONE REG(/details);
  MNAR MODEL (WEEK52/MODELOBS=(TRTP='Placebo'));
RUN;
```

Step 2 - The 200 multiple imputation datasets with imputed and observed data will be analyzed separately using the ANCOVA method separately as described in [Section 6.6.1.2.3.5](#). The LSMean and corresponding SE for the change from baseline in PUL total score at Week 52 will be estimated.

Step 3 - The SAS PROC MIANALYZE will be used to derive the final estimates and test statistics summarizing the 200 dataset results.

The combined treatment difference of LSMean, corresponding SE and 95% CI for the estimated change from baseline in PUL total score at week 52 will be presented.

#### 6.6.1.2.5. Pattern Mixture Models under MNAR for Missing Data: Delta-Adjusting (Tipping Point) Analysis

##### 6.6.1.2.5.1. Estimand Strategy

Same as [Section 6.6.1.1.1](#)

##### 6.6.1.2.5.2. Population of Interest

Same as [Section 6.6.1.1.2](#)

##### 6.6.1.2.5.3. Intercurrent Event Handling

Treatment discontinuation (such as due to AEs, lost to follow-up, withdrawal by subject, physician decision, protocol deviations, etc.): An alternative assumption is that the missing data for the pamrevlumab treated subjects who discontinue early have a lower expected value than the pamrevlumab subjects remaining in the study, while subjects who discontinue from the placebo arm are assumed to have the same data pattern as placebo subjects remaining in the study. This is often called the delta-adjusting (or tipping point) approach.

Death: same as [Section 6.6.1.1.3](#).

##### 6.6.1.2.5.4. Analysis Variable

Change from baseline in the total score of all PUL assessments at Week 52 (Missing value imputation rules are defined below).

#### 6.6.1.2.5.5. Population summary for treatment comparison

The integrated treatment difference of LSMean, corresponding SE and 95% CI for the change from baseline in PUL total score at week 52 will be presented.

The multiple imputation analysis will be performed as follows.

Step 1 - the missing PUL data will be imputed to derive 200 imputed datasets with non-missing data according to the delta-adjusting data approach.

Sample SAS code:

```
PROC MI DATA=aval OUT=zz SEED=9876783 NIMPUTE=200;
  CLASS TRTP;
  VAR TRTP BASE WEEK16 WEEK28 WEEK40 WEEK52;
  MONOTONE REG;
  MNAR ADJUST (WEEK16 /SHIFT=-## ADJUSTOBS =(TRTP='pamrevlumab'));
  MNAR ADJUST (WEEK28 /SHIFT=-## ADJUSTOBS =(TRTP='pamrevlumab'));
  MNAR ADJUST (WEEK40 /SHIFT=-## ADJUSTOBS =(TRTP='pamrevlumab'));
  MNAR ADJUST (WEEK52 /SHIFT=-## ADJUSTOBS =(TRTP='pamrevlumab'));
RUN;
```

Step 2- The observed and imputed PUL data will be analyzed using the ANCOVA method separately as described in [Section 6.6.1.2.3.5](#) for each of the 200 imputed datasets. The LSMean and corresponding SE for the change from baseline in PUL at week 52 will be estimated.

Step 3- The SAS PROC MIANALYZE will be used to summarize the final estimates and test statistics from the 200 dataset results.

#### 6.6.1.2.6. On-treatment Analysis for Primary Efficacy Endpoint

A sensitivity analysis will be performed for PUL assessed during on-treatment period as defined in [Section 5.3.1.2](#).

##### 6.6.1.2.6.1. Estimand Strategy

Same as [Section 6.6.1.1.1](#)

##### 6.6.1.2.6.2. Population of Interest

Same as [Section 6.6.1.1.2](#)

##### 6.6.1.2.6.3. Intercurrent Event Handling Strategy

Same as [Section 6.6.1.1.3](#)

##### 6.6.1.2.6.4. Analysis Variable

Only on-treatment PUL assessments will be included in the analysis

##### 6.6.1.2.6.5. Population Summary for Treatment Comparison

If linear assumption was met, the RCM linear regression model as described in [Section 6.6.1.1.5](#) will be performed; otherwise, ANCOVA model as described in [Section 6.6.1.2.3.5](#) will be performed.

#### **6.6.1.2.7. Per-Protocol Set Analysis for Primary Efficacy Endpoint**

##### **6.6.1.2.7.1. Estimand Strategy**

Same as [Section 6.6.1.1.1](#).

##### **6.6.1.2.7.2. Population of Interest**

PPS as defined in [Section 5.2.3](#).

##### **6.6.1.2.7.3. Intercurrent Event Handling Strategy**

Same as [Section 6.6.1.1.3](#).

##### **6.6.1.2.7.4. Analysis Variable**

Same as [Section 6.6.1.1.4](#).

##### **6.6.1.2.7.5. Population Summary for Treatment Comparison**

If the linear assumption was met, the RCM linear regression model as described in [Section 6.6.1.1.5](#) will be performed; otherwise, the ANCOVA model as described in [Section 6.6.1.2.3.5](#) will be performed.

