#### 6.6.1.1.5. Population Summary for Treatment Comparison

Treatment difference of Least-square mean (LSMean) and SE at week 52 and corresponding 95% CI will be presented.

The random coefficient linear regression model (RCM), where within-patient errors follow a random coefficient regression model will be performed. The RCM model will include fixed effects of time, treatment, treatment-by-time interaction, with baseline ordinal PUL entry score as covariate. The time in the RCM model will be calculated as the elapsed weeks (considered as a continuous variable with 1 decimal place) from first dose date (or randomization date for subjects who drop out prior to any study medication) to the assessment date. All valid values including from unscheduled visits will be included.

The residual plot from the PROC MIXED output will be examined. If the residual plot shows a systematic pattern rather than a random scatter, then the linearity assumption may not be appropriate. In case of non-linearity, MMRM will be used as the primary analysis method, which is currently listed as one of the sensitivity analyses in next section.

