#### **6.6.4. Subgroup Analyses of Specified Endpoints**

The subgroups may include but are not limited to,

- Age group ( $\leq 16$  years,  $> 16$  years),
- Race (White, Others),
- Corticosteroids use (Deflazacort, Prednisone/Prednisolone).
- Baseline PUL level ( $\leq$  Median,  $>$  Median)
- Baseline PUL entry Item A score ( $=1$ ,  $>1$ )
- Baseline PUL entry Item A score (2-5, 1 or 6)
- Regional subgroups:
  - US, Non-US
  - China, Non-China

The primary endpoint PUL will be repeated for relevant and appropriate subgroups. If linear assumption was met, the RCM linear regression model as described in [Section 6.6.1.1](#) will be performed for subgroup analysis; otherwise, MMRM model as described in [Section 6.6.1.2.1](#) will be performed. Secondary endpoints ppFVC, Mid-level of PUL, grip strength, and LVEF will also be analyzed by subgroups.

If subjects who took the prohibited medications constitute to more than 10% of the population, then the subgroup analysis – with or without prohibited medications will be performed.

The LSMeans of treatment difference and corresponding 95% CI will be presented in a forest plot.

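### If linearity fails, the primary analysis falls back to MMRM but the on-treatment and per-protocol checks fall back to ANCOVA, so each comparison mixes a model change with the data change

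*SAP*

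**What the plan says.** The primary model is a random coefficient model (RCM), linear in time. SAP 6.6.1.1.5 sets the trigger for leaving it: "If the residual plot shows a systematic pattern rather than a random scatter, then the linearity assumption may not be appropriate". It then names the replacement: "In case of non-linearity, MMRM will be used as the primary analysis method".

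The other analyses of the primary endpoint that depend on this trigger split into two groups.

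- **To MMRM.** The ITT check (6.6.1.2.2.5) takes its whole specification from 6.6.1.1.5 and so follows the primary. The subgroup analyses (6.6.4) say "otherwise, MMRM model as described in" Section 6.6.1.2.1.
- **To ANCOVA.** The on-treatment section (6.6.1.2.6.5) says the RCM "will be performed; otherwise, ANCOVA model as described in" Section 6.6.1.2.3.5. The per-protocol section (6.6.1.2.7.5) says it "will be performed; otherwise, the ANCOVA model as described in" the same section.

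Section 6.6.1.2.3.5 belongs to a sensitivity analysis planned in its own right: "Multiple Imputation Analysis of Covariance model (MI ANCOVA) will be performed to evaluate the robustness of the primary analysis as a sensitivity analysis". It has three steps: impute 200 datasets, fit an ANCOVA of Week 52 change in each, and combine the results.

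The on-treatment and per-protocol sections both keep the intercurrent-event handling of 6.6.1.1.3, under which missing values after discontinuation are imputed implicitly, assuming MAR. SAP Section 7, which lists the changes from the protocol, gives no reason for the different fallback.

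**The concern.** An on-treatment or per-protocol analysis is informative when the data change and the method does not. If the primary has moved to an MMRM and these two have moved to an ANCOVA, a gap from the primary may come from either source, and agreement may hide two effects that cancel.

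The second issue is missing data. An MMRM uses every visit of a subject who lacks a Week 52 score, which is what implicit handling under MAR requires. An ANCOVA of Week 52 change, fitted without imputation, drops that subject altogether. The two sections do not say which is meant. The trigger is a visual judgement with no numeric criterion, so this branch could well be used.

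**Working it through.** **1. The plan's own figures.** Inputs from SAP 3.3: difference 2.0, SD 2.9, two-sided alpha 0.05, power 90%, 1:1 allocation. The normal approximation gives n per arm = 2(1.960 + 1.282)² × 2.9² / 2.0² = 44.2, so 45 per arm, 90 in total. The exact noncentral-t calculation gives 46 per arm, 92 in total, as stated. At 82 subjects the noncentral-t power is 87.0%, which matches the 87% in SAP Section 7 and the statement of at least 85% in SAP 3.3. None of these depends on the fallback in the two checks.

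**2. Does the reference to 6.6.1.2.3.5 include imputation?** The jump-to-control (6.6.1.2.4.5) and tipping-point (6.6.1.2.5.5) sections cite the ANCOVA method of the same section. Each sets out its own imputation as Step 1 and borrows only the ANCOVA step. On that usage the reference means the ANCOVA alone. The on-treatment and per-protocol sections give no imputation step, so their text leaves the matter open.

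**3. Who is lost from the on-treatment ANCOVA without imputation?** The Week 52 muscle-function window opens on Day 324 (SAP Appendix 2, Table 9). On-treatment data are taken to end 4 weeks after the last infusion (SAP 5.3.1.2). 324 − 28 = 296. A subject whose last infusion was before about Day 296 has no on-treatment Week 52 score and drops out of the model, with any Week 16, 28 and 40 scores. Later stoppers can have one, because Protocol 4.4 requires muscle function tests at the early termination visit 28 days after the last infusion.

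**4. Size.** The documents give no dropout rate, so this is an illustration. Assumptions, with t = week/52:

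- 82 subjects, visits at Weeks 16, 28, 40 and 52
- non-linear mean change −3t² on placebo, treatment effect 2.0t²
- residual SD 2.9√t, correlation 0.75 between adjacent visits, falling geometrically with visit separation
- a standardised baseline covariate with effect 0.5t
- monotone dropout, more likely after a worse score
- 300 trials per setting, with all three methods applied to the same data

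The MMRM had an unstructured covariance by arm. The MI ANCOVA was computed as the point-estimate limit of sequential regression imputation.

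| Missing at Week 52 | Mean: MMRM | Mean: ANCOVA with MI | Mean: ANCOVA, no MI | Sampling SD, MMRM | SD of MMRM minus MI | SD of MMRM minus no MI |
|---|---|---|---|---|---|---|
| 0% | 1.966 | 1.966 | 1.966 | 0.594 | 0.104 | 0.104 |
| 12.2% | 2.041 | 2.035 | 1.978 | 0.654 | 0.123 | 0.218 |
| 22.4% | 1.949 | 1.931 | 1.864 | 0.727 | 0.152 | 0.288 |

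- Mean gap without imputation: 2.041 − 1.978 = 0.063 and 1.949 − 1.864 = 0.085. Monte Carlo standard errors are 0.218/√300 = 0.013 and 0.288/√300 = 0.017.
- Mean gap with imputation: 2.041 − 2.035 = 0.006 and 1.949 − 1.931 = 0.018.
- Within-trial scatter from the model swap alone, relative to the sampling SD: without imputation 0.218/0.654 = 33% and 0.288/0.727 = 40%; with imputation 0.123/0.654 = 19% and 0.152/0.727 = 21%.
- Correlation with the MMRM estimate: 0.945 and 0.922 without imputation, 0.982 and 0.978 with it.

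**5. Per-protocol set.** SAP 5.2.3 requires at least 24 doses and excludes anyone who terminated treatment or study early, so few members should lack a Week 52 score and step 3 hardly applies. The set is drawn from all randomized subjects, while the primary uses the mITT, which leaves out entry score 1. Comparing the two therefore changes the population under any model.

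**The case against.** A reader might infer that these two checks cannot show whether the primary result is robust. The documents do not support that, for four reasons.

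- The mismatch arises only if linearity fails. Otherwise the primary, on-treatment and per-protocol analyses all use the RCM.
- The plan contains a partial bridge. MI ANCOVA is run in the mITT on on-study data. MMRM against MI ANCOVA there isolates the model; MI ANCOVA there against an on-treatment ANCOVA isolates the data.
- The ITT check keeps the primary model.
- If the reference to 6.6.1.2.3.5 carries its imputation steps, the two methods nearly agree. That reading is reasonable: the whole section is cited, and imputation would fit the MAR handling that both checks retain.

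What stands is narrower. The bridge isolates the data effect only if the on-treatment ANCOVA is also multiply imputed, which the SAP does not say. It is weaker for the per-protocol set, whose population differs. How the SAP uses the same reference in the jump-to-control and tipping-point sections supports the reading without imputation at least as well.

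One more caution applies to step 3. SAP 5.3.1.2 joins its two conditions with 'or', and read literally that could admit all on-study data. The loss of subjects assumes the 4-week limit is meant to bind.

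**Conclusion.** The inconsistency is real and unexplained: for one trigger, three analyses of the primary endpoint go to MMRM and two go to ANCOVA. Under non-linearity, comparing either of the two with the primary mixes a model change with the data change.

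For the on-treatment check the expected size is small. Under the assumed dropout of 12% to 22% at Week 52, it is about 0.06 to 0.09 PUL points on average without imputation (within-trial SD 0.22 to 0.29), and at most 0.02 with imputation (SD 0.12 to 0.15, or 0.10 with nothing missing). These figures depend on the assumed covariance, curve and dropout mechanism. For the per-protocol check the point is mainly consistency, and it would be wrong to carry the dropout figures over to that set.

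This is a minor improvement to supportive analyses. The primary test, alpha, power and sample size do not change.

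**What to change.** In SAP 6.6.1.2.6.5 and 6.6.1.2.7.5, replace the ANCOVA fallback with the MMRM as described in Section 6.6.1.2.1. This is the fallback already used in 6.6.1.1.5 and 6.6.4. It settles the imputation question and keeps the earlier on-treatment visits of subjects who stopped.

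If ANCOVA is deliberate, give the reason, say whether the imputation steps apply, and name the mITT MI ANCOVA as the comparator.

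The cost is two phrases in the SAP. No new method is needed, because the MMRM is already specified. The change does not remove the population difference between the per-protocol set and the mITT, which the report should state when it presents that check.
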